## ACCOMPANEERS STUDY DETAILED PROTOCOL

### I. BACKGROUND AND SIGNIFICANCE

#### a. Historical Background

Community health workers (CHWs), a term broadly applied to trained lay health workers, play an important role in health systems worldwide. CHWs have been viewed as an essential component of primary level health care since the Alma Ata declaration of 1978, and have played a crucial role in combatting the HIV epidemic. Randomized trials have documented the efficacy of CHWs in improving adherence to therapy among HIV patients in the developing world, as well as disease-specific outcomes such as CD4 count and HIV viral load.

Non-communicable diseases (NCDs) such as diabetes and hypertension are the leading cause of death worldwide, and disproportionately affect the developing world. According to the WHO, 63% of deaths worldwide in 2008 were due to NCDs, but 80% of NCD deaths occurred in the developing world. The United Nations views renewed focus on NCD control as a public health necessity.

Depression is a leading cause of disability worldwide, and at least half of affected people do not receive effective treatment for depression. Even when effective pharmacologic treatment is delivered, between one and two thirds of patients do not respond to the first antidepressant prescribed, and high relapse and recurrence rates are common.

CHWs offer a potentially lower-cost, culturally sensitive option to help care for patients with NCDs and depression in the developing world.

#### b. Previous pre-clinical or clinical studies leading up to, and supporting the proposed research

CHWs have been shown to be associated with improvement in a number of disease metrics in patients with NCDs in the US, particularly among medically underserved populations. Observational data support improvements in patient knowledge, positive lifestyle changes, self-care, healthcare utilization, adherence to therapy and hemoglobin A1c among patients with diabetes and hypertension in the US. Recent years have seen several domestic randomized controlled trials showing clinically and statistically significant improvement in A1c, healthcare utilization and medication adherence among diabetic patients, as well as improvements in cholesterol, blood pressure and A1c in patients attending urban health centers.

CHWs have also been shown to be effective in the treatment of depression in rural settings, particularly when trained in basic psychoeducation. Their impact on medication adherence is less well established.

Data from the developing world are lacking. To our knowledge, this study will be the first systematic assessment of the impact of CHWs vs. routine care for patients with NCDs in the developing world. As such, it will directly address World Health Organization and United Nations calls for advancement of care of patients with NCDs in the developing world.

Compañeros en Salud (CES) is an affiliate project of Partners in Health, an international non-governmental organization with extensive experience in the use of CHW interventions to help patients to manage chronic disease. Since February 2012, CES has been working in the Sierra Madre region of rural Chiapas, Mexico, in partnership with the local Ministry of Health, to rehabilitate and staff existing government primary care clinics. Each community's clinic is staffed by one CES project physician year-round. CES activities span the range of primary care, but the focus of the project is in the prevention, detection, diagnosis and management of NCDs. At the time of study initiation, CES operated in six rural communities; they expanded to four additional communities after the study began (two were added August 2014, and two more February 2015). Routine care for NCDs is based on national guidelines and consists of monthly in-clinic visits by primary care physicians. Routine care of major depressive disorder includes monthly in-clinic visits, psychoeducation, and daily medications when indicated.

## ACCOMPANEERS STUDY DETAILED PROTOCOL

CES has conducted several community outreach programs to identify community members living with NCDs, including an active case finding program consisting of door to door visits at every home in the catchment area of CES clinics. Screening activities include a risk factor questionnaire for diabetes and hypertension as well as in-home blood pressure screening and referral for blood glucose and blood pressure screening when indicated. They also include screening for depression, and referral for diagnosis in the clinic when indicated. This approach allows diagnosis of chronic disease in an environment in which patients traditionally seek care only for acute illness, and has allowed for diagnosis of a majority of patients living in project communities with hypertension or diabetes. These patients have been started on treatment and are being followed by CES physicians in the clinics in a monthly basis.

In July 2012, CES piloted a CHW program utilizing CHWs locally called “Acompañantes” (aka. Accompaneers, in English) in one of its project communities to augment care of patients with NCDs. Accompaneers are lay health workers, nominated by their communities, who bridge the gap between project clinics and patients, improving patients’ understanding of NCDs, their treatments, and the importance of adherence to therapy. CES physicians offer participation in the Accompaneer program to patients diagnosed with hypertension, diabetes, and depression, in addition to other diseases requiring daily therapy. Accompaneers conduct regular home visits to educate patients, support medication adherence, identify barriers to accessing care, and ensure the timely supply of medications. They are trained using a series of standardized educational sessions, and CES supervisors provide oversight. To date, over 80% of patients with NCDs have opted for the support of an Accompaneer. In our pilot community, the CES physician report fewer treatment interruptions, greater disease literacy and improved clinic attendance in the Accompaneer pilot community.

Plans for Expansion: Based on the observed impact of the pilot phase of the Accompaneer program on improving the adherence to treatment for patients with chronic diseases and its correlation with clinical outcomes, CES plans to expand the program to all project villages. **We will take advantage of this pre-planned programmatic expansion to prospectively evaluate this intervention, which is planned to continue indefinitely, regardless of study findings.**

**c. Rationale behind the proposed research, and potential benefits to patients and/or society**

Unique Opportunity for Evaluation: CHW interventions have been an important part of many health care systems throughout the world. Unfortunately, they are often implemented without systematic evaluation of their impact. CES’s programmatic plan for phased expansion of the Accompaneers program offers a natural opportunity to study the intervention in a prospective, systematic manner.

Potential Programmatic Benefits for CES: This study will help to evaluate the impact of a CHW intervention to improve the care for patients with NCDs and depression. Support for a CHW intervention would serve as a cornerstone for programmatic expansion within CES to improve the quality of care of patients with NCDs within the program catchment area. Furthermore, this study may provide evidence for cross-site implementation of similar programs within the broader network of Partners in Health, as well as in other areas of Mexico.

Potential Implications for Health Systems: If effective, CHW interventions would offer a means of low-cost, culturally sensitive, integrated care for patients with NCDs in the developing world.

### II. **SPECIFIC AIMS**

**a. Specify objectives and hypotheses to be tested in the research project**

Aim 1. Assess the impact of a CHW intervention on changes in adherence to medications for patients with diabetes, hypertension and depression

## ACCOMPANEERS STUDY DETAILED PROTOCOL

Aim 2. Assess the impact of a CHW intervention on scheduled clinic visit attendance for patients with diabetes, hypertension and depression  
Aim 3a. Assess the impact of a CHW intervention on changes in Hb A1c in diabetic patients  
Aim 3b. Assess the impact of a CHW intervention on changes in systolic and diastolic blood pressure in patients with hypertension  
Aim 3c. Assess the impact of a CHW intervention on changes in Patient Health Questionnaire-9 (PHQ-9) scores among patients with depression  
Aim 4. Assess health beliefs, literacy, and satisfaction with medical care among patients participating in a CHW intervention.

### III. SUBJECT SELECTION

#### a. Inclusion/exclusion criteria

Inclusion criteria:

- Formal diagnosis of Type II Diabetes Mellitus, Stage I or II Hypertension, Major Depressive Disorder, or two or more of the aforementioned diagnoses. Diabetes is defined as a fasting plasma glucose  $\geq 126$ . Hypertension is defined as systolic blood pressure  $\geq 140$  or diastolic blood pressure  $\geq 90$ , observed on at least two separate occasions. Major Depressive Disorder is defined as a diagnosis of Major Depressive Disorder by the clinic physician, following DSM-V diagnostic criteria and scoring a PHQ-9  $\geq 10$ .
- Daily medications prescribed for control of patient's condition at at least one point in time
- Residence within the study catchment area
- Age greater than or equal to 18

Exclusion criteria:

- Known or suspected secondary hypertension. Includes all patients with hypertension due to a comorbid medical condition, such as hyperthyroidism, pheochromocytoma, renal artery stenosis, etc.
- Known or suspected Type 1 diabetes
- Pregnancy-induced hypertension
- Gestational diabetes
- Chronic use of glucocorticoids
- Normal bereavement or complicated grief
- Depressive disorder due to another medical condition
- Substance or medication induced depressive disorder
- Past or present history of mania or hypomania
- Schizophrenia or schizoaffective disorder
- Adjustment disorder with depressed mood

#### b. Source of subjects and recruitment methods

CES physicians maintain a registry of all known patients living with hypertension, diabetes and depression in their communities, as diagnosed by active case finding or through regular clinic visits. All patients meeting inclusion criteria will be prescreened by CES physicians, who are not study investigators, to ask if study staff may approach them for enrollment. Study enrollment will be independent of, and will not affect eligibility for, enrollment in the Acompaneers program.

## ACCOMPANEERS STUDY DETAILED PROTOCOL

### IV. SUBJECT ENROLLMENT

#### a. Methods of enrollment, including procedures for patient registration and/or randomization

Study enrollment will be conducted by trained study staff that are independent of the patient's health care providers and clinical care. In the communities in which we plan to conduct the study, the usual way of approaching someone for a meeting is to approach them at home. Furthermore, it is important to avoid conflating study activities with clinical care, given the limited experience with research studies in these communities. Study staff will therefore go to patients homes to enroll them in the study. Patients declining enrollment in the study will still be eligible for participation in the Accompaneers program when it is introduced to their community.

Safety of study staff will be ensured by working in teams with established itineraries for home visits. In cases of medical emergency, CES physicians operate fully stocked primary care clinics in all project villages, a satellite phone is available in communities for study volunteers, and project cars are available for emergency transportation.

#### b. Procedures for obtaining informed consent (including timing of consent process)

Informed consent will be obtained during a pre-defined study enrollment period. Study staff will approach eligible patients at home or in clinic to solicit consent using a standardized consent form (see attached Study Consent form). Verbal consent will be obtained and documented.

#### c. Treatment assignment, and randomization (if applicable)

Please see Schema (attached) for visual explanation of study procedures.

Randomization: All communities will receive CHW accompaniment programs, but will be randomized at the community level in the order of program rollout. At present, CES only has the capacity to roll the Accompaneers program out to new project villages once every three months. Accordingly, prior to study commencement the order of rollout of the Accompaneers program to each of the project villages (Communities "A" through "D") will be assigned at random. Following data collection in the first four study communities, the remaining four communities will be randomized (Communities "E" through "G").

Patient enrollment in Accompaneers program (specific to enrollment in program, not in research study): When the Accompaneers program is introduced to a community, all eligible patients will be offered the option of participation in the program. Those accepting participation will be introduced to an Accompaneer in the clinic, and program home visits will commence in the week following enrollment.

### V. STUDY PROCEDURES

#### a. Study visits and parameters to be measured (e.g. laboratory tests, x-rays and other testing)

The study will not involve additional clinical study visits. Home visits will be conducted for questionnaire administration, conducted by trained study staff who are not CHWs or CES physicians. These visits will also include point-of-care testing of hemoglobin A1c and blood pressure, which will be recorded on study forms, after which samples will be destroyed; no samples will be sent to laboratories for testing (see section Ve.) Home visits with patients with depression will include questionnaires on adherence only.

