**e. Data to be collected and when the data is to be collected**

Data collection will be conducted by trained study staff that are independent of the patient's health care providers and clinical care. An enrollment questionnaire will be administered at the time of study enrollment (see attached Enrollment Form). Questionnaires related to medication adherence will be administered by study staff prior to study initiation and every three months thereafter until study completion (see attached Adherence Questionnaire, and translated version). Study staff will also conduct assessment of hemoglobin A1c, and systolic and diastolic blood pressure during these visits. Hemoglobin A1c will be assessed using fingerprick point-of-care technology, which gives an immediate result in the patient's presence. Data will be immediately transferred to data collection forms, then deleted from data collection devices and collection strips used to collect blood will be discarded in the patient's presence. No blood samples will be stored or transported as part of this study. These assessments and interviews will take place in the participant's home or the clinic, according to the participant's preference.

The study will involve collection of data from the medical record, which will be achieved by the use of unique patient identifiers linking to medical record numbers. Chart reviews will be conducted by study staff, and will be limited to those data specified in data collection forms (see attached Medical Records Form). No additional data will be collected from the medical record.

Questionnaires related to health beliefs, health literacy, and satisfaction with medical care will be conducted at baseline and at three month intervals after study initiation among selected patients by study staff (see attached Qualitative Supplement, and translated version).

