### **VI. BIOSTATISTICAL ANALYSIS**

**a. Specific data variables being collected for the study (e.g. data collection sheets).**

All study data will be collected using data collection sheets (see attached, per above).

Primary study outcomes:

- Self-report of medication adherence, as derived from study questionnaires adapted from validated measures.

Secondary study outcomes:

- Proportion of scheduled monthly chronic disease appointments attended in preceding three months.
- Systolic and diastolic blood pressure (hypertension patients)
- Hemoglobin A1c (diabetes patients)
- PHQ-9 scores (patients with depression)
- Qualitative assessments of patients' health beliefs, health literacy, and satisfaction with medical care

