#### d. Adverse event reporting guidelines

Because this study does not involve changes in therapeutic medical regimens for participants, it is not anticipated that adverse medical events will occur. Study staff noting hypertensive urgency or emergency will refer patients to CES physicians for treatment. Challenges or complaints from participants regarding study data collection or study staff will be reported to study leadership, and patients will be offered the option of withdrawal from the study. Challenges or complaints in the CHW accompaniment program will be reported to the program leadership, including supervisors of the CHW program, independent of study investigators.

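### Section V.a restricts visits with depression patients to adherence questionnaires, with no exception for those who also have diabetes or hypertension; this conflicts with Section V.e and with Aims 3a and 3b

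*Combined protocol and SAP*

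**What the plan says.** Section V.a describes the home visits. It first gives the general rule, "These visits will also include point-of-care testing of hemoglobin A1c and blood pressure", and refers the reader to Section V.e. It then ends with a specific rule: "Home visits with patients with depression will include questionnaires on adherence only". The specific rule applies to patients who have depression. It does not say whether it means patients who have depression and no other study diagnosis.

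Four other places bear on the point:

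- **Section III.a** makes comorbid patients eligible. The qualifying diagnoses are diabetes, hypertension, depression, "or two or more of the aforementioned diagnoses".
- **Section V.e** sets the adherence questionnaire at baseline and every three months, and adds: "Study staff will also conduct assessment of hemoglobin A1c, and systolic and diastolic blood pressure during these visits". It has no exception for depression.
- **Section II.a** defines Aim 3a in diabetic patients and Aim 3b in patients with hypertension.
- **Section VI.a** lists A1c as an outcome for diabetes patients and blood pressure as an outcome for hypertension patients. Neither is limited to patients without depression.

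**The concern.** For a participant with hypertension and depression, V.a says to give the questionnaire and stop, while V.e says to take a reading. Staff cannot follow both. V.a is the more specific instruction, so a careful team could reasonably follow it.

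If it is followed literally, the missing data are not a random subset. Every participant with diabetes or hypertension who also has depression is unmeasured at every round. Aims 3a and 3b would then describe patients without depression, whereas the protocol enrols, and defines its outcomes for, all diabetic and hypertensive patients. Depression may plausibly be related to adherence and disease control, so the two populations could respond differently. If communities resolve the conflict differently, what is measured would also vary between clusters, of which there are at most eight. A three-monthly reading that was not taken cannot be recovered later.

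**Working it through.** This is mainly a reconciliation of text. The protocol gives no power or precision figure for Aim 3a or 3b, so there is no planned quantity to reproduce.

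**Step 1: apply each section to each type of participant.**

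| Participant | V.a, read literally | V.e | II.a and VI.a |
|---|---|---|---|
| Diabetes or hypertension, no depression | A1c and blood pressure taken | taken | outcome required |
| Depression only | questionnaire only | taken (no exception stated) | not required |
| Depression plus diabetes or hypertension | questionnaire only | taken | outcome required |

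For depression-only patients, V.a can be read as a harmless exception to V.e, because no aim needs their A1c or blood pressure. For comorbid patients that reading fails: treating V.a as the exception removes data that the aims and the outcome list require.

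**Step 2: illustrate the size.** The inputs from Section VI.d are an average of 32 diabetes or hypertension patients per community, 80% participation, and 50 depression patients in communities E to H. The number of rounds follows from V.e (baseline, then every three months) and VI.b (21 months): 1 + 21/3 = 8. The share of the 50 who are comorbid is not given; 10%, 20% and 40% are assumptions.

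- Diabetes or hypertension participants in E to H: 32 × 4 × 0.8 = 102.4, about 102.
- Patients unmeasured = share × 50.
- Fraction lost, p = patients unmeasured / 102.4.
- Standard error ratio = 1/√(1 − p), treating patients as independent and ignoring clustering.
- Patient-rounds lost = patients unmeasured × 8.

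| Assumed comorbid share of the 50 | Unmeasured | p | Standard error ratio | Patient-rounds lost |
|---|---|---|---|---|
| 10% | 5 | 4.9% | 1.03 | 40 |
| 20% | 10 | 9.8% | 1.05 | 80 |
| 40% | 20 | 19.5% | 1.11 | 160 |

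The ceiling in E to H is 50 of 102.4 (49%), reached only if every depression patient were comorbid. No depression count is given for communities A to D, so the calculation cannot be extended to them. The table pools diabetes and hypertension; the fraction lost for A1c alone or blood pressure alone could differ.

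**Step 3: check the primary outcome.** The adherence questionnaire is exactly what V.a retains, so the primary outcome in VI.a is unaffected under either reading.

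**The case against.** The best reply is that the sentence was meant for patients enrolled for depression alone, the one disease group with no point-of-care test. V.e, II.a and VI.a all fit that intention, and only a literal reading of one sentence opposes it. This has force. It means the loss is conditional, and a reader who infers that comorbid patients will certainly go unmeasured goes further than the documents do. But the limiting words are absent, and the protocol writes comorbidity rules when it wants them: Section VI.c sets separate blood pressure thresholds for hypertension with diabetes.

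A second reply is that chart review could supply the values. V.e provides for it, but "Chart reviews will be conducted by study staff, and will be limited to those data specified in data collection forms", and the content of that form is not in the documents. Clinic values would also depend on attendance, which is itself a secondary outcome. The attached schema and forms might settle who is measured; they are not available here.

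Three stronger inferences are tempting, and the documents support none of them:

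- **Measurement stops when depression is diagnosed during follow-up.** Nothing says that visit content changes with a new diagnosis, and no reclassification is described.
- **The loss grows after rollout because Accompaneers find more depression.** Section I.b lists their duties as education, adherence support, identifying barriers and medication supply. It places depression screening in the separate door-to-door case finding.
- **A safety screen is lost.** Section IX.d says "Study staff noting hypertensive urgency or emergency will refer patients to CES physicians for treatment". That covers what staff happen to note. It does not make the study reading a required screen, and routine care already includes monthly physician visits.

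**Conclusion.** The V.a sentence is wrong as written and must be reconciled with V.e. The supported finding is a contradiction over what is measured in eligible patients who have depression together with diabetes or hypertension. Literal compliance with V.a would remove them from Aims 3a and 3b selectively by depression status.

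The size of the loss cannot be determined from the documents. Under the assumed overlaps it is about 5% to 20% of the diabetes or hypertension participants in E to H, with patient-level standard errors about 3% to 11% larger. The change in the population studied matters more than that loss of precision. Severity is moderate: the affected outcomes are secondary, the primary outcome is still collected, and the loss occurs only if staff read V.a literally.

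**What to change.** Replace the last sentence of V.a with wording such as: *When depression is a patient's only study diagnosis, the home visit consists of the adherence questionnaires alone. Participants with diabetes or hypertension, whether or not they also have depression, have the A1c and blood pressure assessments of Section V.e at baseline and at each three-monthly round.*

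Two features of this wording should be kept. It leaves the content of depression-only visits as it is now. It also does not tie A1c to diabetes and blood pressure to hypertension, which V.e does not do and which could end blood pressure readings in participants with diabetes alone. V.e should carry a matching cross-reference.

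If the literal restriction is in fact intended, then V.e, Aims 3a and 3b and the outcome list in VI.a must be limited to patients without depression, and the reason given.

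The cost is small. Study staff already visit these participants and already carry out both measurements in the study, so the addition is a few test strips per round: at most 5 to 20 in E to H under the assumed overlaps. The change needs to be in place before the rounds it covers.
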